Quantitative Sensory Testing: In order to determine pain modulatory balance, all participants will undergo assessment of mechanical pain and conditioned pain modulation (CPM). **Mechanical Pain Procedures:** Pressure pain threshold (PPT) will be assessed on the most painful knee and at up to two unaffected sites ipsilateral to the tested knee, the quadriceps muscle and the trapezius muscle. The examiner will apply a constant rate of pressure and the participant will be instructed to indicate when the sensation first becomes painful. Also, punctate mechanical stimuli will be delivered to the knee and the hand using von Frey hairs, which are nylon monofilaments. This test will involve delivering either one stimulus or a series of 5-10 repeated stimuli and asking participants to report the intensity of pain and unpleasantness experienced. **Conditioned Pain Modulation:** As a measure of pain inhibition, we will test the ability of cold water applied to one hand to diminish the experience of pressure pain on the contralateral trapezius. First, pressure pain threshold will be measured on the trapezius as described above. Then, the participant will immerse his/her opposite hand in a cold water bath at a temperature ranging from 10-12 °C. Subjects will immerse their hand and will report when they first feel pain, then will continue for up to 1 minute or until they wish to stop (whichever comes first). Subjects will be prompted to rate the intensity of the cold-pressor pain at pre-determined times during the test. Approximately thirty seconds into the cold water immersion, pressure pain threshold will again be measured. Upon hand withdrawal, the pressure pain test will be repeated.

Baseline Session 2

In order to reduce costs and permit enrollment of participants in whom neuroimaging may be contraindicated, we plan to conduct neuroimaging in approximately two-thirds of the sample. This is justified, as the effect size for intervention-induced changes in neuroimaging outcome measures is notably larger than for QST and clinical outcomes (see Table 4 below). The participants who will not undergo neuroimaging will be identified as follows.

- 1) Individuals who meet eligibility criteria but are unable to complete imaging due to a contraindication (e.g. claustrophobia, metal implants, body size). We anticipate that this will account for the majority of participants that do not complete neuroimaging.

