D3. Data Analysis: Sample Size and Statistical Power: In this study, we are proposing to randomize 360 individuals to four groups defined by a 2X2 factorial design, and we expect to have 320 completers. Table 4 illustrates the effect sizes (Cohen's D) produced by the proposed interventions compared to their sham conditions for different outcomes that have been reported in our previous studies (4, 5). We plan to conduct six primary hypothesis tests (Sham vs Real BAT and Sham vs. Real tDCS for three primary outcomes) with the use of F-test at a corrected $\alpha=0.0083$ significance level. Even with this conservative approach, we have sufficient power for detecting single intervention effects, with power greater than 90% for most outcomes. We do not have effect size estimates for the

combined effect, but our sample size provides 80% power to detect effects as small as Cohen's $D=0.39$.

Table 4: Effect Sizes Observed for tDCS and MMT in our Previous Work				
		Power for Different Sample Sizes		
Outcome	Cohen's D	N = 300	N = 320	N = 340
tDCS (from Ahn, et al)				
CPM	0.34	0.61	0.65	0.68
Pain Rating	0.44	0.88	0.90	0.92
MMT (from Zeidan, et al)				
Heat Pain	0.51	0.97	0.98	0.99
rCBF	0.82	0.99	0.99	0.99

Statistical Analysis Plan:

Summary statistics will be calculated by group for demographic characteristics and all predictor and outcomes measures at baseline and follow-up. Statistical inference will be conducted for the three primary aims as follows.

For **Aim 1**, we will test the effects of BAT, tDCS, and their interaction upon outcomes. For hypotheses 1a-1c, our primary outcomes will be pain modulatory balance (ratio of CPM to temporal summation), pain-evoked cerebral activation, and clinical pain, respectively. Intention-to-treat analysis will be conducted using appropriate linear contrasts to test for intervention effects accounting for interaction terms based on general linear models with covariate adjustment for site, sex, age, and baseline value. Specifically, for each outcome (Y), the model will be:

$$E(Y) = \beta_0 + \beta_1 \text{BaselineScore} + \beta_2 \text{Covariates} + \beta_3 \text{BAT} + \beta_4 \text{tDCS} + \beta_5 \text{AA} +$$

$$\beta_6 \text{BAT} * \text{tDCS} + \beta_7 \text{BAT} * \text{AA} + \beta_8 \text{tDCS} * \text{AA} + \beta_9 \text{BAT} * \text{tDCS} * \text{AA},$$

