Missing Data and Sensitivity Analysis: The four randomized groups will be compared in missing patterns in the primary outcomes including reasons for missing data, timing of missing data, and distributions of baseline covariates and earlier outcomes.

We will consider the following approaches to impute each of the primary outcomes: (1) the last-observation-carried-forward method; (2) missing primary outcome predicted by a fitted regression model using demographic and baseline clinical variables; (3) missing primary outcome predicted by baseline and available follow-up outcomes on a fitted regression model. The imputation method for the primary intent-to-treat analysis will be selected using cross-validation performed on the participants with complete data. Specifically, we will evaluate imputation accuracy based on 2,000 repetitions that randomly leave out 20% of the complete samples. In addition, to consider the uncertainty due to missing values, we will apply the SAS multiple imputation procedure to generate multiple imputed data sets using the selected imputation approach, and combine results from analyses of these data sets, e.g., to provide mean and variance of the treatment effect estimates. No imputation is planned for secondary outcomes. Missing data in secondary outcomes will be considered missing. For a subject to achieve a given secondary endpoint, that endpoint must be observed.

7. Possible Discomforts and Risks:

Potential risks are minimal and relate primarily to short-term discomfort of the sensory testing procedures delivering cold and mechanical pressure. The risks from brain imaging procedures are thought to be minimal in appropriately screened participants. Questionnaires include specific questions about how a participant feels and ask the participant to think about life experiences. Reading or answering these questions may cause some participants embarrassment or discomfort.

Potential Risks

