Mechanical pressure: pressure is delivered by a hand-held algometer (spring-controlled device delivering calibrated pressure via a flat 10mm diameter rubber tip). Pressure is delivered at an approximate rate of 30 kPa/sec. Participants will be instructed to signal by pressing a button when the pressure sensation first becomes painful at which time the researcher removes the algometer. There is little opportunity for bruising or other transient trauma from this procedure. Also, mechanical punctate stimuli will be delivered using a nylon monofilament. Risk associated with this procedure is minimal.

Cold Stimulation: Cold is delivered by having subjects immerse their hand in cold water. This can produce temporary discomfort, which subsides with withdrawal of the hand. No other risks are known. Participants may stop at any time.

Magnetic resonance imaging (MRI): MRI is a procedure that allows doctors to look inside the body by using a scanner that sends out a strong magnetic field and radio waves. This procedure is used routinely for medical care and is very safe for most people, but participants will be monitored during the entire MRI scan in case any problems occur. The risks of MRI are:

- The MRI scanner contains a very strong magnet. Therefore, participants may not be able to have the MRI if they have any type of metal implanted in their body, for example, any pacing device (such as a heart pacer), any metal in their eyes, or certain types of heart valves or brain aneurysm clips. A MRI technologist will question participants about any contraindications before they enter the scanner.
- There is not much room inside the MRI scanner. Participants may be uncomfortable if they do not like to be in close spaces ("claustrophobia"). During the procedure, participants will be able to talk with the MRI staff through a speaker system, and, in the event of an emergency, participants can tell them to stop the scan.
- The MRI scanner produces a loud hammering noise, which has produced hearing loss in a very small number of participants. Participants will be given earplugs to reduce this risk, and headphones for added protection.
- If an obvious abnormality is discovered during the participant's MRI scan, they will be informed about it by the research team, and will be provided with a copy of the MRI scan and we will encourage them to see their primary care physician. MRI will only be done for research purposes in this study.

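### The plan does not say which threshold reading defines CPM in the H1a outcome; if it is the one taken during immersion, the stated imputation does not name the data best suited to early hand withdrawal

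*Combined protocol and SAP*

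**What the plan says.** The Statistical Analysis Plan in D3 states: "our primary outcomes will be pain modulatory balance (ratio of CPM to temporal summation), pain-evoked cerebral activation, and clinical pain, respectively". CPM is therefore half of one of the three primary outcomes, and the D3 model adjusts each outcome for its baseline value.

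Under Conditioned Pain Modulation (D2.1, Baseline Session 1), the trapezius threshold is measured first. The opposite hand then goes into a "cold water bath at a temperature ranging from 10-12 °C". Participants report first pain and "then will continue for up to 1 minute or until they wish to stop (whichever comes first"). Section 7 repeats the point: "Participants may stop at any time". No minimum immersion time is set.

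Two further threshold readings follow:

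- "Approximately thirty seconds into the cold water immersion, pressure pain threshold will again be measured".
- "Upon hand withdrawal, the pressure pain test will be repeated".

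Neither D2.1 nor D3 says which of these enters CPM, or what happens when the hand comes out before the first of them.

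The Missing Data and Sensitivity Analysis section lists three ways to impute a primary outcome: last observation carried forward; "missing primary outcome predicted by a fitted regression model using demographic and baseline clinical variables"; and a regression on baseline and available follow-up outcomes. The choice among them is made by cross-validation in participants with complete data, and multiple imputation is then run with the chosen approach.

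**The concern.** The two candidate readings measure different things in a participant who withdraws early.

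- **During-immersion reading.** It exists only for people still immersed at about 30 s. Withdrawal is a response to the cold stimulus, so the missing values are unlikely to be a random subset.
- **Withdrawal reading.** Everyone can have it, but it follows anything from a few seconds to 60 s of conditioning. A treatment that raises cold tolerance would change that exposure.

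Leaving the definition open would, on its own, be a matter of missing detail. What makes it a statistical point is that the stated imputation fits the first case poorly. It does not name the one pressure reading taken just after conditioning in the same person, nor how long the hand stayed in, nor the arm. It also speaks only of outcomes, although a participant who withdraws early at baseline has no baseline CPM for the model. The estimated BAT and tDCS effects on H1a could then be diluted.

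**Working it through.** **1. The plan's own figure.** Table 4 gives power 0.65 for CPM at D = 0.34 and N = 320. With noncentrality 0.34 × √(320/4) = 3.04 and two-sided α = 0.0083, a noncentral t gives 0.650, so it reproduces. The other two entries also reproduce: 0.613 at N = 300 (stated 0.61) and 0.684 at N = 340 (stated 0.68).

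**2. When the during-immersion reading is complete.** Section 7 says: "Pressure is delivered at an approximate rate of 30 kPa/sec". A ramp begun at 30 s ends at 30 + threshold/30 seconds. The documents give no thresholds. Assumed values of 150, 300 and 450 kPa give 35, 40 and 45 s.

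**3. What the three imputation options can draw on.** The activity schedule in D1 places sensory testing at Visits 1 and 7 only, and the monthly follow-ups are questionnaires. For CPM this means:

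- Carrying forward can only repeat the baseline value, and it has nothing to carry if that is missing too.
- The demographic and baseline regression contains no same-session information.
- The follow-up regression has no later CPM to use. Whether it would admit the withdrawal reading is unclear.

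The cross-validation compares these options only in people who tolerated the bath.

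**4. Dilution from leaving out arm.** If a share m of analysed outcomes is imputed without arm, those values carry on average no arm difference, so the estimate is roughly 0.34 × (1 − m).

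| Assumed case | m | Estimate |
|---|---|---|
| 3% missing post-treatment | 0.03 | 0.34 × 0.97 = 0.330 |
| 10% early withdrawal per visit, missing baselines excluded, 14% lacking at least one reading | (0.14 − 0.10)/0.90 = 0.044 | 0.34 × 0.956 = 0.325 |
| 20% early withdrawal per visit, missing baselines excluded, 27% lacking at least one reading | (0.27 − 0.20)/0.80 = 0.0875 | 0.34 × 0.9125 = 0.310 |

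The 14% and 27% come from a simulation with 10-20% early withdrawal per visit.

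**5. Adding selection.** Assume a tolerance-CPM correlation of 0.4 and a treatment that raises tolerance by 0.3-0.5 SD. With 10-20% early withdrawal per visit, simulation of the stated imputation gives about 0.29-0.33 for a true 0.34. I re-ran it with baseline-to-post correlations of 0.5-0.7 (CPM) and 0.7-0.8 (tolerance), excluding missing baselines, and obtained 0.28-0.32, in line with that range. At 3% withdrawal the re-run gave 0.33-0.34.

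**6. The alternative.** Imputing both visits from the withdrawal reading, immersion time and arm gives about 0.34-0.35 under the same assumptions. In the re-run this needed an indicator for completing the full minute, because immersion time is capped at 60 s. With capped time entered as a straight line only, the estimate overshot, to as much as 0.37.

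**The case against.** Several stronger readings are tempting, and the documents do not support them.

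- *Early withdrawers have no reading after conditioning.* They do. The repeat on hand withdrawal is not tied to reaching 30 s.
- *CPM requires more than 30 s in the bath, so data must be missing.* This follows only if the during-immersion reading defines CPM, which is not stated. If the withdrawal reading defines it, the missing-data argument falls away and only the variable exposure remains.
- *Power for H1a falls.* Dropping 5, 10, 20 or 30% of the 320 completers takes the Table 4 CPM row to 0.62, 0.59, 0.52 or 0.45. The arithmetic is right, but the plan imputes primary outcomes rather than dropping people. That row is also for CPM under tDCS, not for the ratio outcome. These are not expected consequences.
- *Missingness differs by race or arm.* The background reports ethnic differences in pain facilitation and inhibition, not in cold-immersion tolerance. This is a plausible inference, not a documented fact.

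It can also fairly be said that the missing-data section names classes of predictors rather than a closed list, and that it already compares the four groups on why and when primary outcomes are missing. The bias is conditional too. In complete cases, with no treatment effect on tolerance, the estimate stays at about 0.34; with a tolerance gain and the assumed positive correlation, it understates benefit rather than inventing it.

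What stands is that the defining reading is unstated, early withdrawal has no rule, a missing baseline CPM is not covered, and the withdrawal reading, immersion time and arm are not named in the imputation. Comparing missingness patterns describes the problem without correcting it.

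**Conclusion.** The point holds in a limited form. The plan leaves open which reading defines CPM, and each choice has a consequence it does not address: informative gaps for the during-immersion reading, or unequal exposure for the withdrawal reading. In the first case the stated imputation is weaker than one built on data the protocol already collects, plus immersion time.

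The size is modest. A true 0.34 SD effect would be estimated at about 0.29-0.33 if 10-20% withdraw early at each visit, and almost unchanged at about 3%. This rests on an assumed withdrawal rate, a tolerance-CPM correlation of 0.4 and a treatment-related gain in tolerance, none of which the documents give. It also treats the 0.34 for CPM as a stand-in for the ratio, which has no stated effect size. The point is worth considering; it does not threaten the trial.

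**What to change.** 1. State in D3, before unblinding, which threshold reading or readings define CPM and how withdrawal before the during-immersion reading is handled.
2. Record immersion time at baseline and post-treatment.
3. If the during-immersion reading is chosen, impute it at both visits within the planned multiple imputation, using the same-session withdrawal reading, immersion time (with an indicator for the full minute) and treatment arm. Extend the missing-data section to a missing baseline CPM.
4. Add one sensitivity analysis that uses the withdrawal reading for everyone.
5. Report early withdrawals by arm and race.

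The bath temperature and the right to stop stay as they are. The cost is SAP wording, one recorded time per immersion and one extra analysis, with no new procedure or participants. The downside is that the imputation assumes the withdrawal reading predicts the during-immersion reading in early withdrawers, who by definition have no during-immersion reading with which to check it.

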where BAT and tDCS are dummy variables for interventions, AA is the dummy variable for African Americans. Linear contrast will be employed to test the main effect of BAT (corresponds to the test of $\beta_3 + \beta_6/2 + \beta_7/2 + \beta_9/4=0$) and tDCS (test of $\beta_4 + \beta_6/2 + \beta_8/2 + \beta_9/4=0$). These six tests (2 main effects for three primary outcomes) will be performed at one-sided $\alpha=0.0083$ significance level. In addition, point estimates and 95% confidence intervals will be obtained for the BAT and tDCS effects with or without the presence of the other treatment in the whole population or within AA and NHW subgroups. We will use normal probability plots to assess distributional assumptions of the models. The above analysis plan will be followed for other outcomes including resting state cerebral blood flow, disability and functional performance, as well as the analysis of changes of the outcomes from post-treatment to three-month follow-up.

For **Aim 2**, we will assess interactions between race and intervention. Point estimates and 95% confidence intervals will be obtained for the race difference in the effects of BAT and tDCS on each outcome. Because we expect the interaction effect to be smaller than the main effect, for formal hypothesis testing, we plan to pool evidence across three primary outcomes to test the ethnic group differences. Specifically, we will obtain a p-value corresponding to test the hypothesis $\beta_7=\beta_8=\beta_9=0$ for

each outcome based on the general linear model specified in the analysis plan for Aim 1. And Fisher's combination of three p-values will be used as the overall test statistic, which will be compared to the null distribution obtained through permutation of ethnic group variable.

For Aim 3, path models with strictly ordered relationships will be used to study the interventions' direct effects on clinical pain and disability and the indirect effect on the mediating variables including pain modulatory balance; resting state and stimulus-evoked pain-related brain function; perceived stress, pain catastrophizing, and mindfulness. We will construct additional analyses using pre-treatment variables as predictors of intervention effects. We will examine separate multivariable models for each ethnic group to determine whether mediators of treatment effects differ for AAs vs. NHWs.

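### Imaging power is shown only at the full sample size although about two-thirds are scanned, and the larger-effect argument for scanning fewer is supported for BAT but not for tDCS

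*Combined protocol and SAP*

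**What the plan says.** Section D3 (Sample Size and Statistical Power) says "We plan to conduct six primary hypothesis tests": real versus sham for each of BAT and tDCS, on three primary outcomes, "with the use of F-test at a corrected $\alpha=0.0083$ significance level". The Statistical Analysis Plan names the outcomes as pain modulatory balance, pain-evoked cerebral activation and clinical pain. Cerebral activation therefore carries two of the six primary tests. The same plan says that the six tests "will be performed at one-sided $\alpha=0.0083$ significance level".

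On numbers, D3 randomizes 360 and states "we expect to have 320 completers". Table 4 gives power at N = 300, 320 and 340 only. Its single imaging row, listed under MMT, reads "rCBF 0.82 0.99 0.99 0.99". The tDCS block has two rows, CPM (D = 0.34) and pain rating (D = 0.44), and no imaging row. After noting that no effect size is available for the combined effect, D3 adds that "our sample size provides 80% power to detect effects as small as" D = 0.39.

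Section D2.1 (Baseline Session 2) says "we plan to conduct neuroimaging in approximately two-thirds of the sample". It defends this by reference to Table 4: "This is justified, as the effect size for intervention-induced changes in neuroimaging outcome measures is notably larger than for QST and clinical outcomes".

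**The concern.** The power section and the imaging section use different sample sizes. D3 reports one sensitivity for the trial's sample and an imaging row at the full N, while D2.1 removes about a third of participants from that outcome. Neither section gives power at the number scanned.

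The defence of the smaller N rests on a larger imaging effect. The only such effect in Table 4 belongs to one intervention: I read MMT as the mindfulness training, that is, BAT. Both interventions have a primary imaging test, so the argument is carried over to tDCS without a figure behind it.

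What is at stake is interpretation. Section D2 describes changes in brain function and pain modulatory balance as the main mechanistic interest. A null tDCS or combined result on cerebral activation could be read against a sensitivity of D = 0.39 at 80% power, which the scanned subset does not have.

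**Working it through.** **Inputs.** Alpha = 0.05/6 = 0.0083 (D3). A factorial main effect compares N/2 with N/2 (2×2 design, equal cells, Table 1). Completers: 320 (D3). Effect sizes: Table 4. Fraction scanned: about two-thirds (D2.1).

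**Formula.** F-test with 1 and N − 2 degrees of freedom and noncentrality λ = D²N/4. Power is the probability that this noncentral F exceeds the central critical value at alpha.

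**Step 1: reproduce the plan's figures (two-sided F).**

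| Row | D | Printed (300/320/340) | Recomputed |
|---|---|---|---|
| tDCS, CPM | 0.34 | 0.61/0.65/0.68 | 0.61/0.65/0.68 |
| tDCS, pain rating | 0.44 | 0.88/0.90/0.92 | 0.87/0.90/0.92 |
| MMT, heat pain | 0.51 | 0.97/0.98/0.99 | 0.96/0.97/0.98 |
| MMT, rCBF | 0.82 | 0.99/0.99/0.99 | above 0.99 throughout |

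For D = 0.39 at N = 320, λ = 0.1521 × 320/4 = 12.17 and power is 0.797, so the stated 80% reproduces. A one-sided test at 0.0083 does not fit: it gives 0.859 for this figure and 0.736 for CPM at N = 320, where 0.65 is printed. The power section is therefore two-sided in effect, at the full 320.

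**Step 2: number scanned.** 2/3 × 320 = 213. Two-thirds of 360 with 10% attrition is 216. Two-thirds of 360 without attrition is 240. Two-thirds of Table 4's columns (300, 320, 340) is 200, 213 and 227.

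**Step 3: D = 0.39 at the scanned N.** At 213, λ = 0.1521 × 213/4 = 8.10. At 240, λ = 9.13.

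| N | Two-sided F, 0.05/6 | One-sided, 0.0083 | D at 80% power, two-sided |
|---|---|---|---|
| 320 | 0.797 | 0.859 | 0.39 |
| 213 | 0.573 | 0.667 | 0.48 |
| 216 | 0.581 | 0.674 | 0.48 |
| 240 | 0.641 | 0.728 | 0.45 |

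As a check, the detectable D scales with the square root of N: 0.391 × √(320/213) = 0.48 and 0.391 × √(320/240) = 0.45.

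**Step 4: the two imaging tests separately.**

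- BAT, D = 0.82: power is 0.999 at 200 and above 0.999 at 213 and 227. The printed 0.99 entries would not change.
- tDCS: the documents give no imaging effect size. As an assumption only, at 213 scanned (two-sided), power is 0.43 at D = 0.34, 0.71 at D = 0.44 and 0.80 at D = 0.48. The first two D values are the tDCS effects that Table 4 gives for CPM and pain rating.

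**The case against.** **The 0.39 is not an imaging figure.** This stands. D3 attaches it to the combined effect in the whole sample, so a reader who infers that the plan claims 80% power for the tDCS imaging test goes beyond the text. What remains is that the sentence makes no exception for imaging, that Hypothesis 1 expects the largest effects from the combination with cerebral blood flow among its outcomes, and that any imaging contrast can use only scanned participants. The contrast is itself unclear: 0.39 reproduces as half versus half, whereas real-plus-real against sham-plus-sham (80 versus 80) has power of about 0.42 at D = 0.39 even before imaging losses.

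**The smaller N is disclosed and defended.** This stands for BAT, whose imaging test loses nothing that matters. It does not extend to tDCS.

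**57% is the low end.** This also stands. Over 213 to 240 scanned and both versions of the test, the range is 57% to 73%. Adjustment for the baseline value would raise power: with an assumed baseline-outcome correlation of 0.5 (none is given), power at 213 is 0.73 two-sided or 0.81 one-sided. Table 4 reproduces without such adjustment, so 57% is the like-for-like restatement, not a forecast for the fitted model.

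**A reader might infer that the tDCS imaging test is underpowered.** The documents do not support that. Setting its effect equal to the tDCS behavioural effects gives 43% to 71% at 213. Scaling those effects by Table 4's imaging-to-heat-pain ratio for MMT (0.82/0.51) gives D of about 0.55 to 0.71 and power of 0.91 to 0.99. Both are assumptions.

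**Table 4 also lacks BAT rows for CPM and clinical pain.** True, but those outcomes are not measured in a reduced sample on the strength of the table.

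**Conclusion.** The point holds as a mismatch between the stated sensitivity and the number scanned, together with a justification that covers one of two interventions. For imaging, power at D = 0.39 is about 57% (213 scanned) to 64% (240) on the test that reproduces Table 4, against 80% at N = 320. Under the one-sided test it is 67% to 73%, against 86%. The detectable D at 80% two-sided power rises from 0.39 to about 0.48 or 0.45. These figures assume a half-versus-half contrast, no covariate gain, and two-thirds applied either to completers or to all those randomized.

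The conclusion does not reach the BAT imaging test. Nor does it show that tDCS imaging power is low; the plan simply gives no effect size from which to compute it. The flaw lies in what the plan states about power, not in the design, and it should be corrected because cerebral activation is a primary outcome.

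**What to change.** 1. In D3, state the expected number scanned and label the rCBF row with it (about 200, 213 and 227 in place of 300, 320 and 340). The entries stay at 0.99.
2. Limit the D = 0.39 figure to outcomes measured in all 320 completers and say which contrast it refers to. Add that the imaging main effect detectable with 80% power is about D = 0.48, or 0.45 if 240 are scanned. Settle whether the primary tests are two-sided F-tests or one-sided, and compute all power figures on that basis.
3. In D2.1, limit the larger-effect justification to BAT and state that no tDCS imaging effect size is available. Show tDCS imaging power at the scanned N over a range of D labelled as an assumption, for example 43% at 0.34, 71% at 0.44 and 80% at 0.48 with 213 scanned (two-sided).

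No new rule is needed for reading a null tDCS imaging result: the analysis plan already provides point estimates and 95% confidence intervals for the BAT and tDCS effects, and a cross-reference would do.

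The cost is some wording and a relabelled table row, with no extra participants or scans. The downside is a less favourable stated sensitivity for imaging.

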mechanistic interest is in capturing changes in brain function and pain modulatory balance induced by the interventions. Thus, this research includes aspects of Stage 0 (basic science to inform intervention development) and Stage 1 (modification and refinement of existing interventions) intervention development (50). Subjects. A total of 360 individuals with knee OA (180 AA, 180 NHW) will be enrolled in the study. We anticipate a 10% attrition rate, given the brief duration of the intervention, which will yield a final sample size of at least 320 participants. In our pilot trial of tDCS, attrition was much lower (2.4%)(4); however, in this larger two-site study, we account for the possibility of increased attrition. As during the current funding cycle, both community-based and clinic-based recruitment methods will be utilized at both study sites with similar inclusion-exclusion criteria as in our prior and ongoing work. Initial Screening. All participants will undergo a knee OA screening interview that shows 87% specificity and 92% sensitivity for detecting knee OA (51). The screening will also assess demographic and health history information to ensure that no exclusion criteria are present. Eligible individuals will be scheduled for baseline assessment at the study site. Demographic Measures. Ethnic group will be determined by participant self-report using the standard Health and Human Services categories. We will recruit adults who self-identify as either Black/African American or non-Hispanic white (NHW) as their primary ethnic/race group. Socioeconomic Status (SES): Because ethnic/race groups often differ in SES (52), and lower SES has been associated with increased risk of clinical pain (53, 54), including increased prevalence of arthritis (55, 56), we will obtain measures of SES.

D2.1. Baseline Assessment: Two baseline visits will occur in the six weeks before the intervention. The first baseline session will assess: health history, cognitive function, clinical pain and function and QST measures. The second baseline session will involve brain imaging. In order to distribute participant burden, some questionnaires will be completed online between the first 3 sessions, while others will be completed during the two pre-treatment sessions. The following questionnaires will be completed during the pre-treatment phase of the protocol.

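### The fixed 0.0083 for all six primary tests is valid but less efficient than Holm's step-down; the gain depends on the other tests, and the sidedness must be settled first

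*Combined protocol and SAP*

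**What the plan says.** The power paragraph of section D3 states: "We plan to conduct six primary hypothesis tests (Sham vs Real BAT and Sham vs. Real tDCS for three primary outcomes"). They are to be done "with the use of F-test at a corrected" level of 0.0083, which is 0.05/6. The plan calls this conservative and adds: "Even with this conservative approach, we have sufficient power for detecting single intervention effects", with power above 90% for most outcomes.

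Table 4 gives four effect sizes with power at N = 320:

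- tDCS on CPM: D = 0.34, power 0.65
- tDCS on pain rating: D = 0.44, power 0.90
- mindfulness training on heat pain: D = 0.51, power 0.98
- mindfulness training on rCBF: D = 0.82, power 0.99

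The Aim 1 paragraph of the Statistical Analysis Plan names the three primary outcomes: pain modulatory balance (the CPM to temporal summation ratio), pain-evoked cerebral activation, and clinical pain. It then says: "These six tests (2 main effects for three primary outcomes) will be performed at one-sided" 0.0083. No step-down or other sequential procedure appears in either place.

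**The concern.** Under a fixed threshold, every test pays the full price for six comparisons even after several others have been clearly rejected. The plan expects some large effects (0.82 and 0.44 on quantities tied to primary outcomes). In that setting a step-down rule can relax the threshold for the remaining tests without raising the family-wise error.

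The row with least power in Table 4, tDCS on CPM, is the only planning figure for tDCS on pain modulatory balance. Section D2 says the main mechanistic interest is change in brain function and pain modulatory balance, so this row bears on a core hypothesis. At stake is some power for the smaller effects, at no cost in participants. Validity is not in question.

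**Working it through.** **Inputs (section D3 unless stated).** Six tests; per-test level 0.05/6 = 0.00833; "randomize 360 individuals to four groups defined by a 2X2 factorial design, and we expect to have 320 completers", so each main effect compares 160 with 160. Effect sizes are those of Table 4. Neuroimaging is planned in about two-thirds of the sample (Baseline Session 2), so I assume 2/3 × 320 ≈ 213 for the imaging tests.

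**Step 1: reproduce Table 4.** The mean of the test statistic is D × √N / 2. For D = 0.34 and N = 320 it is 0.34 × 17.889 / 2 = 3.041.

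- Two-sided critical value at 0.00833: 2.638. Power = 1 − Φ(2.638 − 3.041) = 0.656. The F distribution with 1 numerator df gives 0.650. The plan prints 0.65.
- One-sided critical value at 0.00833: 2.394. Power = 1 − Φ(2.394 − 3.041) = 0.741. This does not match the plan.

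All twelve Table 4 entries reproduce within two points on the two-sided reading. So does the statement of 80% power at D = 0.39 (0.802 normal, 0.797 with the t distribution). Table 4 is therefore two-sided, and the Aim 1 paragraph is not.

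**Step 2: which of the six effects are stated.** Two Table 4 rows correspond closely to primary tests: tDCS on pain rating (0.44) and mindfulness on rCBF (0.82). CPM (0.34) is a component of the pain modulatory balance ratio and serves as its proxy. Heat pain is not a primary outcome. That leaves three tests with no stated effect: tDCS on cerebral activation, BAT on pain modulatory balance, and BAT on clinical pain.

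**Step 3: Holm.** Order the six p-values and compare them in turn with 0.05/6, 0.05/5, 0.05/4, 0.05/3, 0.05/2 and 0.05, stopping at the first failure. I simulated six normal test statistics (400,000 draws, independent tests, N = 320, imaging N = 213). Power for the D = 0.34 test:

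| Other five effects | Two-sided: Bonferroni → Holm | One-sided: Bonferroni → Holm |
|---|---|---|
| None real | 0.66 → 0.66 | 0.74 → 0.74 |
| Only 0.44 and 0.82 real | 0.66 → 0.71 | 0.74 → 0.79 |
| 0.44 and 0.82, three unstated at 0.34 | 0.66 → 0.80 | 0.74 → 0.88 |
| All five others rejected | 0.66 → 0.86 | 0.74 → 0.92 |

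Two rows can be checked by hand. With all five others rejected, the last test is run at 0.05, so two-sided power is 1 − Φ(1.960 − 3.041) = 0.860. With exactly two others rejected, it is run at 0.05/4 = 0.0125, which gives 0.707. Within-treatment correlation of 0.3 or 0.5 moves the third row by about one point and the others by less.

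**Step 4: error control.** In scenarios with true nulls, Holm's simulated family-wise error was 0.039 to 0.049.

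**The case against.** Bonferroni is valid and openly described. The plan prints 0.65 for the CPM row and claims power above 90% only for most outcomes. It says this is not an efficacy trial and plans estimates with 95% intervals. A fixed threshold also keeps each decision independent of the others and has simple matching simultaneous intervals. All of this stands, and it is why the point is an efficiency suggestion. The argument from intervals is weak here, because the planned 95% intervals do not correspond to tests at 0.0083 in any case.

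A reader might infer that Holm would lift the CPM test to a definite 74% to 84%. The documents do not support that. Two-sided, 0.74 requires heat pain (0.51) to stand in for BAT on pain modulatory balance with the other two unstated effects null. About 0.84 requires those two to be 0.44. Without the stand-in and with the unstated effects null, the figure is 0.71.

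A reader might also propose simply switching to two-sided Holm. Against the one-sided rule in the Aim 1 text that could lose power: 0.71 against 0.74 when only the 0.44 and 0.82 effects are also real. For example, a one-sided p of 0.006 passes at 0.0083, but its two-sided value of 0.012 fails Holm's first two steps (0.0083 and 0.010). The guarantee that Holm rejects everything Bonferroni rejects holds only at the same sidedness.

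Nor is tDCS on CPM proven to be the weakest primary test. If the unstated tDCS effect on imaging were 0.34 in 213 participants, its two-sided Bonferroni power would be 0.44.

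**Conclusion.** This is a cheap improvement and not an error in the plan. At one stated sidedness, Holm controls the family-wise error at 0.05 under any dependence and is never less powerful than the fixed 0.0083.

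For D = 0.34 at N = 320 the two-sided gain runs from nothing to about 20 points (0.66 to 0.86). It is 5 points if only the two effects tied to primary outcomes also hold, and about 14 points if the three unstated effects are each 0.34. One-sided, the same scenarios start from 0.74 and reach 0.74, 0.79 and 0.88, with a ceiling of 0.92.

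These figures assume that CPM stands in for the pain modulatory balance ratio, that imaging N is 213, and that the Table 4 effects carry over to this trial. A reader might infer that primary hypotheses will be failed needlessly under the present rule. That is too strong, since the gain is zero if no other effect is real and the documents do not state three of the six effects.

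**What to change.** 1. Reconcile the F-test in the power paragraph, which is two-sided and is the basis of Table 4, with the one-sided 0.0083 in the Aim 1 paragraph. State one sidedness in both places. If one-sided is kept, recompute Table 4.
2. At that sidedness, replace the fixed threshold with one sentence: the six primary p-values are tested by the Holm step-down procedure at family-wise 0.05 (0.05/6, 0.05/5, 0.05/4, 0.05/3, 0.05/2, 0.05).
3. Keep Table 4, at the sidedness chosen, labelled as power at the first step (the worst case). If a Holm figure is quoted, state the effects assumed for the other five tests.

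The cost is a short SAP edit, made before unblinding, with no change to sample size or visits. The one drawback is that simple Bonferroni-level confidence intervals will not always agree with the step-down decisions, and the SAP should say so.
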